Patients with progressive disease after two cycles (defined as a clear increase in bone marrow blast count, typically a > 50% increase in bone marrow blasts over baseline) should be removed from study.

Patients with stable disease may continue on study and should undergo a diagnostic bone marrow biopsy at the end of even numbered cycles.

Once AML patients achieve morphologic complete remission with incomplete blood count recovery (CRi) or MDS patients achieve a marrow complete response (Marrow CR) as defined in Section 9.0, decitabine administration may be decreased to 20 mg/m²/day for ten consecutive days every 6 weeks, to limit myelosuppressive toxicity and improve count recovery. After 2 cycles at 6 week intervals, the dose may be reduce to 20 mg/m²/day for five consecutive days in 6 week cycles, at the discretion of the treating physician. After two cycles of five consecutive days of treatment, if the patient meets the definition of CR with complete cytogenetic response as defined in Section 9.0, administration may further be decreased to three consecutive days per cycle at the discretion of the treating physician.

Sample collection for correlative studies:

Bone marrow biopsies should be performed at baseline, at Cycle 1 Day 10 ± 1, and at Day 28 ± 4 of Cycles 1, 2, 4, and 6. Following Cycle 6, bone marrow biopsies should be performed at the discretion of the treating physician to assess for relapse or progression.

Peripheral blood samples should be collected on Day 4± 1 of Cycle 1. Collection should be obtained 45 ± 15 minutes after decitabine infusion is initiated.

Genomic Predictors of Decitabine Response in AML/MDS

Table of Contents

Section	Page
Section 4.21.0 INTRODUCTION	7
1.1 Rationale.....	7
1.2 Decitabine and Hypomethylating agents in AML/MDS.....	9
1.2.1 Pharmacokinetics and Metabolism of Decitabine.....	11
1.2.2 Experience with extended dosing schedules.....	12
1.3 Correlative Studies	13
2.0 OBJECTIVES.....	15
2.1 Primary Objective.....	15
2.2 Secondary Objectives	15
3.0 PATIENT SELECTION.....	16
3.1 Inclusion Criteria	16
3.2 Exclusion Criteria.....	16
3.3 Inclusion of Women and Minorities.....	17
4.0 REGISTRATION PROCEDURES	18
4.1 Confirmation of Patient Eligibility.....	18
4.2 Patient Registration in the Siteman Cancer Center Database.....	18
4.3 Assignment of UPN.....	18
5.0 INVESTIGATIONAL PLAN	20
5.1 Summary of Study Design.....	20
5.2 Study Procedures	20
5.2.1 Pre-study Procedures.....	20
5.2.2 Baseline Evaluation.....	21

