Because all patient-specific exome-discovered mutations will be assessed a second time in the primary bone marrow sample as well as the Cycle 1 Day 10 \pm 1, Cycle 1 Day 28 \pm 4, and Cycle 2 Day 28 \pm 4 bone marrow samples, this study will also serve to validate all exome-discovered mutations. This is important, because exome sequencing is associated with a 20-50% false-discovery rate depending on type I error tolerated (mutation-calling algorithms are typically set for greater sensitivity than specificity). Thus, many mutations discovered during exome sequencing are incorrect. This second analysis of these mutations will server to exclude these false positive calls.

3. To correlate the bone marrow expression profile from pre-study and Cycle 1 Day 10 \pm 1 with response to decitabine.

We will correlate expression signatures, and changes in expression signatures, with:

- Achievement of clinical CR,
- Mutation status.

4. To correlate steady-state plasma decitabine concentration on Cycle 1 Day 4 \pm 1 with:
 - Achievement of CR.

5. To correlate the extent of bone marrow DNA hypomethylation on Cycle 1 Day 10 \pm 1 with response to decitabine.

We will assess the percent reduction in bone marrow methylcytosine content using LC-MS. Patients will be evaluated pre-study and Cycle 1 Day 10 \pm 1. The change in DNA methylcytosine content will be correlated to:

- Achievement of clinical CR,
- Change in expression signature.

This will determine whether inadequate blast exposure to decitabine correlates with drug resistance.

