A power analysis was performed using Chi-square test for the association between mutation and response to decitabine. The frequency of *DNMT3A*, *IDH1/2*, and *TET2* mutations in AML and MDS patients are each between 15% and 30% in multiple cohorts.[29-37] **Table 3** shows the minimal detectable differences of response rates between mutant and wild-type cases, assuming an expected overall 45% CR/CRi rate and 80% power. For an average of 20% frequency of a mutated gene, for example, 100 patients will provide 80% power to detect 30% difference at a 2-sided 0.1 alpha error. The purpose of this study is to determine whether any of these mutations result in a clinically significant association that would warrant pre-treatment testing. We believe that a reasonable cut off would be if at least 30% of clinical response could be attributed to the presence of a specific mutation. However, we anticipate that more power could be achieved as we assess patient groups with combined characteristics (e.g. *DNMT3A* mutation or loss of *DNMT3A* expression). In addition, we

Table 3. Detectable mutation associated response rates (80% power, $\alpha = 0.05$)

Total N	% of patients with a given mutation	Detectable response difference	Sensitivity of mutation to predict response at minimum detectable response difference*
100	15%	0.40	80%
	20%	0.35	75%
	30%	0.30	67%
	40%	0.27	61%
	50%	0.26	58%

* Assuming the overall response rate (CR/CRi) of 45%

expect that the majority of the enrolled 125 patients can be used in the analysis (since all of our molecular information will be acquired within 30 days of enrollment, we anticipate a drop-out rate of 20% or less).

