14.2.3 Secondary Endpoint Analyses

The overall response rate (CR/CRi/PR) and complete response rate (CR/CRi) will be compared with historical controls[2], and the 95% confidence intervals will be provided.

The rate of patient specific mutation clearance after 10, 28, and 56 days of therapy will be determined using an Illumina based platform. We will compare the rate of mutation clearance between the patients who achieve a CR/CRi after 4 cycles and those who do not. We anticipate that we will identify between 6 and 25 exonic SNVs per case (the range obtained with >200 AML samples sequenced to date with whole genome or exome sequencing), and that the expected 95% confidence

interval of the mean variant allele frequency will be $\pm 2.56\%$ and $\pm 1.25\%$, respectively, if we assume an anticipated standard deviation of 3.2% within the same clone. The change of tumor burden over time and its association with clinical response will be assessed using 2-way ANOVA for repeated measurement data, followed by the ad-hoc multiple comparisons for between-group differences (e.g., responders vs. non-responders) at given time points as well as the between-time differences within each group. The resultant critical P values will also be corrected using permutation analysis for multiple testing.

The steady-state plasma decitabine concentration on day 4 ± 1 will be measured and correlated with clinical overall response.

The percent decrease in bone marrow methylcytosine will be calculated on day 10 ± 1 . We will compare this reduction with previously published data and between the patients who achieve CR/CRi and those who do not. The correlation of peak plasma levels of decitabine with response will be assessed using 2-sample t-test or Mann-Whitney non-parametric rank-sum test as appropriate. The change of total bone marrow DNA methylcytosine from baseline and its association with both steady-state plasma drug levels and response will be assessed using 2-way ANOVA for repeated measurement data, followed by the ad-hoc multiple comparisons for between-group differences (e.g., responders vs. non-responders) and between-time differences. Similar analyses will be performed for the correlation of expression profiles and SNP analysis with pharmacokinetic data.

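### The repeated-measures ANOVA planned for tumor clearance needs complete marrow series through Day 56, and the 20% drop-out allowance does not cover that marrow

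*Combined protocol and SAP*

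**What the plan says.** Section 14.2.3 (Secondary Endpoint Analyses) plans to determine "The rate of patient specific mutation clearance after 10, 28, and 56 days of therapy". It compares that rate "between the patients who achieve a CR/CRi after 4 cycles and those who do not". The longitudinal analysis is then named: "The change of tumor burden over time and its association with clinical response will be assessed using 2-way ANOVA for repeated measurement data". It is followed by comparisons between groups at given time points and between time points within groups.

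Section 1.3 lists the four marrows: pre-study, Cycle 1 Day 10, Cycle 1 Day 28 and Cycle 2 Day 28. It defines velocity of response as a natural-log rate of allele-frequency clearance.

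On losses, section 14.2.2 says "we anticipate a drop-out rate of 20% or less", and gives the reason: "since all of our molecular information will be acquired within 30 days of enrollment". Section 14.1 defines three populations but assigns none to the clearance analysis. Section 14 contains no complete-case rule, imputation, mixed model or sensitivity analysis for a patient whose marrow series is incomplete.

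Section 5.3 lets death or confirmed progression end treatment at any time. The Study Schema also removes "Patients with progressive disease after two cycles".

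**The concern.** Classical two-way repeated-measures ANOVA needs a value at every time point. A patient with three of the four marrows contributes nothing to it, although the three samples were taken by an invasive procedure. The last marrow falls around Day 56, outside the 30-day window used to justify the drop-out figure, and a patient who dies or stops before then may not have it.

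The method also treats each visit as a fixed category, while real sampling days will vary. Section 6.0 tolerates delays of up to 8 weeks between cycles. Section 5.2.9 moves the marrow to day 42 for responders on 6-week cycles. A patient who moved to 6-week cycles from Cycle 2 would have that marrow near day 28 + 42 = 70, whereas a patient on 28-day cycles would have it near day 56. The ANOVA would treat the two as the same visit, and the shift applies only to patients who are responding.

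Velocity and depth of clearance come first in the list of secondary biomarkers in section 2.2. At stake are the precision of the responder contrast and, under some patterns of loss, its size.

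**Working it through.** **1. The plan's own figures reproduce.**
- Enrollment: 100 / (1 − 0.20) = 125.
- Confidence-interval half-widths for mean allele frequency: 1.96 × 3.2/√6 = 2.56 and 1.96 × 3.2/√25 = 1.25, as stated.
- Clearance power, two-sample t-test, two-sided 0.05. With SD 3.2: 99.8% (6 variants, 10-point difference) and 98.6% (3 variants, 15 points). With SD 4.7: 91.2% and 82.8%. The plan states >99%, >98%, 91% and 82%.

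In these power figures n is the number of variants in a clone, not the number of patients. They therefore do not show what happens when patients are lost from the responder comparison.

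**2. Complete series.** There are three post-baseline marrows. The documents give no loss rate, so let m be an assumed fraction missing at each visit. If visits are lost independently, the complete fraction is (1 − m)³. If the same patients are missing at every visit, it is 1 − m.

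| m | Independent: (1 − m)³ | Of 125 | Same patients: 1 − m | Of 125 |
|---|---|---|---|---|
| 5% | 86% | 107 | 95% | 119 |
| 10% | 73% | 91 | 90% | 112 |
| 15% | 61% | 77 | 85% | 106 |

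Under independence, 100 of 125 is missed once (1 − m)³ < 0.80, that is, m > 1 − 0.80^(1/3) = 7.2%. If the same patients are missing throughout, it is missed only above 20%. Loss by death or progression is monotone, so the truth probably lies between the two columns.

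**3. Precision.** If loss is proportional in the two groups, the standard error of the contrast grows by √(100/n) relative to the planned 100: √(100/91) = 1.05 and √(100/77) = 1.14.

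**4. Possible bias.** An illustrative simulation used 45 responders and 55 non-responders (the evaluable split in section 14.2.3), marrows at days 0, 10, 28 and 56, and 200 trials per scenario. Assumed values: slopes of −0.04 and −0.01 per day on log allele frequency, between-patient slope SD 0.012, residual SD 0.25. The true Day 56 difference is 0.03 × 56 = 1.68. About 20% of all patients lacked the Day 56 marrow, and half of those also lacked Day 28. In scenarios where only non-responders are lost, that is 20/55 = 36% of them.

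| Loss depends on | All data | Complete series | Shrinkage |
|---|---|---|---|
| Nothing (random) | 1.683 | 1.683 | 0 |
| Response group only | 1.698 | 1.692 | about 0 |
| Slow observed early clearance among non-responders | 1.689 | 1.561 | about 8% |
| Unobserved slope among non-responders | 1.676 | 1.464 | about 13% |

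At 10% loss the last two rows shrink by about 3% (1.694 to 1.650) and 5% (1.675 to 1.590). I quote no mixed-model estimates because only 12 data sets per scenario were fitted, too few to be informative.

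**The case against.** The strongest reply is that the plan never says incomplete patients are dropped. It names a method, with no complete-case rule and no covariance structure. It also plans contrasts at individual time points, which can use everyone sampled at that visit, and velocity and depth are per-patient summaries that do not by definition need four marrows. A reader who infers that the plan excludes every patient with a missing marrow goes beyond the text. What stands is that the named method does this in its classical form, and nothing in the plan says otherwise.

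A reader might also infer that the missing marrows will be mostly early deaths and progressions. The documents give no such figure. The Study Schema removes progressors after two cycles, about when the last marrow is due, so they need not lack it. An end-of-study marrow is scheduled too. However, section 5.2.10 omits correlative studies from it while footnote d of Appendix 2 includes them at all time points, so it is not a dependable substitute.

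Nor do the documents show that the contrast is biased. Loss that depends only on response group costs precision and leaves the contrast unbiased, as the second simulated scenario shows. It would also be wrong to apply the plan's 20% at each visit, because that figure is overall drop-out.

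Finally, the point does not extend to methylcytosine, although the same ANOVA is named there ("steady-state plasma drug levels and response will be assessed using 2-way ANOVA for repeated measurement data"). Section 1.3 says "Patients will be evaluated pre-study and Cycle 1 Day 10", so there are only two marrows. With two time points the group-by-time test is a t-test on change, and a mixed model recovers almost nothing. Power is also ample. The stated 99% (45 versus 55, 20-point difference, SD 15) reproduces as above 99.99% two-sided. It stays above 99.9% at 45 versus 35 and is 99.3% at 45 versus 15.

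**Conclusion.** The point holds for tumor clearance only. The planned ANOVA is a poor match for a four-marrow series with unequal and variable sampling days. The plan does not say how incomplete series are handled, and its drop-out rationale stops before the last marrow.

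The size depends on assumptions that the documents do not supply. Independent loss of 5% to 15% per visit leaves 107 to 77 complete series of 125; concentrated loss leaves 119 to 106. Shrinkage of the responder contrast ranges from 0 to about 13% at 20% loss, and is non-zero only where loss is related to clearance within a response group. The claims that patients are certain to be dropped, that the comparison is certain to be biased, or that the methylcytosine comparison is affected are not supported.

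This is a secondary biomarker analysis and the primary mutation–response test is untouched. The change is still worth making because it is cheap and uses samples already collected.

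**What to change.** In section 14.2.3, for tumor clearance:

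- Replace the two-way repeated-measures ANOVA with a linear mixed model on log variant allele frequency, the scale on which section 1.3 defines velocity. Fixed effects are response group, time and their interaction. Use all observed marrows, actual sampling days, and an unstructured or time-based covariance. State how values at or below the detection limit enter, since the log of zero is undefined.
- Keep the planned contrasts at each time point.
- Add a sensitivity analysis for death or progression before the Cycle 2 marrow. The mixed model does not remove bias from loss that depends on clearance nobody observed.
- Name the analysis population, and tabulate missing marrows by visit and reason.

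In section 14.2.2, correct the 30-day justification so that the drop-out allowance also addresses the Day 56 marrow, or state that it applies only to the earlier molecular data.

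For methylcytosine, keep the analysis and report the number of missing Day 10 marrows with reasons.

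The cost is SAP wording and slightly more analysis work. No extra patients, samples or visits are needed.

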Statistical power justification. A power analysis was performed using two-sample t-test for between-group difference and paired t-test for the change over time. For tumor clearance, this will provide $> 99\%$ power to detect a 10% difference in the means at two separate time points for clones with 6 or more variants, and $> 98\%$ power to detect a 15% difference if there are 3 or more variants per clone with $\alpha = 0.05$ (power will decrease to 91% and 82%, respectively, in cases where the standard deviation is 4.7%, the maximum we have observed thus far). For pharmacologic correlations, we anticipate 85% power to determine a 25 ng/ml difference between the average C_{\max} of 45 evaluable responders and 55 evaluable non-responders with an anticipated average C_{\max} of 70 ng/ml and a standard deviation of 40 ng/ml within the entire cohort, and with $\alpha = 0.05$. [22] We believe a less significant difference would not be sufficient to warrant application in clinical decision making (i.e. whether to continue therapy for more than 1 cycle). We anticipate 99% power to determine a difference of 20% in the reduction of bone marrow methylcytosine between 45 evaluable responders and 55 evaluable non-responders with an expected standard deviation of 15% and $\alpha = 0.05$. [28, 66-68] The difference in methylcytosine reduction previously observed was 30% between patients achieving CR/PR and those with only hematologic improvement. [28]

Time to relapse and time to death will also be listed for each patient.

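### Section 14.2.3 tests a continuous plasma decitabine level against methylcytosine change with a two-way repeated-measures ANOVA, which cannot take a continuous concentration unless it is grouped; no groups or cut-point are given

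*Combined protocol and SAP*

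**What the plan says.** Section 14.2.3 covers three links among plasma decitabine, marrow methylcytosine and response.

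- **Plasma level and response.** "The steady-state plasma decitabine concentration on day 4 ± 1 will be measured and correlated with clinical overall response". The method is also named: "The correlation of peak plasma levels of decitabine with response will be assessed using 2-sample t-test or Mann-Whitney non-parametric rank-sum test as appropriate". Concentration is the outcome here and stays continuous.
- **Methylcytosine change with plasma level and with response.** One method is named for the two links together: "association with both steady-state plasma drug levels and response will be assessed using 2-way ANOVA for repeated measurement data". The contrasts to come after it are then listed: "followed by the ad-hoc multiple comparisons for between-group differences (e.g., responders vs. non-responders) and between-time differences". Response is the only grouping offered as an example. No concentration bands, cut-point, covariate, correlation or regression is named for the drug-level part.
- **Extension.** "Similar analyses will be performed for the correlation of expression profiles and SNP analysis with pharmacokinetic data".

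Plasma is sampled once, on Cycle 1 Day 4 ± 1 (section 5.2.5). Its assumed mean is 70 ng/ml, with "a standard deviation of 40 ng/ml within the entire cohort". For methylcytosine, section 1.3 says "We will assess the percent reduction in bone marrow methylcytosine content using LC-MS", with samples pre-study and on Cycle 1 Day 10 ± 1. The power paragraph of 14.2.3 covers responders against non-responders and change over time. It gives no power for plasma level against methylcytosine.

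**The concern.** An ANOVA followed by between-group contrasts needs categorical factors. Time and response are categorical; a drug concentration is not. Time, response and drug level would also make three factors, not two. Someone must therefore decide at analysis how concentration enters. The choice most in keeping with the stated method is to form groups, at a cut that could be picked after seeing the data.

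Grouping discards information. A null result from grouped data could then be read as showing no relation between exposure and the pharmacodynamic effect when the data could have shown one. The extension to expression profiles carries the same gap into a much larger set of tests.

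**Working it through.** **1. The plan's own figures.** Inputs from 14.2.3: 45 responders, 55 non-responders, alpha 0.05 (two-sided assumed).

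- Plasma: difference 25, SD 40, so d = 25/40 = 0.625. The noncentrality is 0.625/√(1/45 + 1/55) = 3.11, and t-test power is 86.8% against the stated 85%. The Mann-Whitney version (efficiency 0.955) gives 85.3%.
- Methylcytosine: d = 20/15 = 1.33, noncentrality 6.63, power above 99.9% against the stated 99%.

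Both reproduce. Neither concerns plasma level against methylcytosine.

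**2. What repeated measures contribute.** With one baseline and one Day 10 value, the group-by-time test is the same as a test on the change. The comparison is therefore between a correlation with the change using continuous concentration and the same association after grouping.

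**3. Median split, normal levels, N = 100.** Continuous power is Φ(√(N−3)·atanh(r) − 1.96), plus a negligible opposite tail. A median split multiplies r by √(2/π) = 0.798.

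Example at r = 0.20: √97 × atanh(0.20) = 9.849 × 0.2027 = 2.00, giving 51.5%. After the split r becomes 0.160, and 9.849 × 0.1610 = 1.59, giving 35.4%.

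| True r | Continuous | Median split | Loss (points) |
|---|---|---|---|
| 0.10 | 16.7% | 12.4% | 4 |
| 0.15 | 31.9% | 22.0% | 10 |
| 0.20 | 51.5% | 35.4% | 16 |
| 0.25 | 71.1% | 51.3% | 20 |
| 0.267 | 76.9% | 56.8% | 20.1 (maximum) |
| 0.30 | 86.2% | 67.2% | 19 |
| 0.35 | 94.9% | 80.7% | 14 |
| 0.40 | 98.7% | 90.3% | 8 |
| 0.45 | 99.8% | 95.9% | 4 |
| 0.50 | >99.9% | 98.6% | 1 |

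Simulation gave losses of 16, 21, 19, 13 and 7 points at r = 0.20, 0.25, 0.30, 0.35 and 0.40. The maximum hardly moves with sample size: 20.3 at N = 80 and 19.9 at N = 125. Tertiles lose up to about 20 points and quartile groups about 23.

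**4. Where larger losses come from.** An uneven 25/75 cut multiplies r by 0.734, with a maximum loss of 27.2 points. Log-normal levels with the plan's mean and SD (CV 40/70 = 57%), a relation linear on the raw scale and a median split multiply r by 0.709, with a maximum loss of 30.0. Some skew is likely: a normal curve with mean 70 and SD 40 puts Φ(−70/40) = 4% of levels below zero.

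**5. Should response be in the model?** Suppose plasma and methylcytosine are related only because both differ by response, by the amounts in step 1. The covariance is 0.45 × 0.55 × 25 × 20 = 123.75. Then r = 123.75/(40 × 15) = 0.206 if 15% is the total SD. If 15% is the within-group SD, the total is √(225 + 0.2475 × 400) = 18 and r = 123.75/(40 × 18) = 0.172. Simulated power is 42 to 56% for the unadjusted correlation, but 5% (that is, alpha) for the concentration slope adjusted for response. Adding response would remove the association being looked for.

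**The case against.** The plan never says the concentration will be cut. A reader might infer a planned dichotomisation; the text does not support that. It is silent, and concentration could enter as a covariate in a repeated-measures ANCOVA or mixed model. This stands, but a covariate model is not the two-way ANOVA with group contrasts that is named, so the wording needs changing either way.

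A reader might also infer a fixed, large loss of power. The documents give no correlation between the two measures and no distribution for the plasma level, so the loss may be negligible or about 20 points. The 27 to 30 point cases need an uneven cut or marked skew. Even there the full loss is not recovered in practice: at r = 0.276 with log-normal levels, a log-scale analysis has 73% power and Spearman 65%, against 50% for the split. The gains are 23 and 15 points.

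The third stronger reading is that section 1.3 depends on this analysis, because it says "This will determine whether inadequate blast exposure to decitabine correlates with drug resistance". That sentence follows a list correlating methylcytosine change with clinical CR and with change in expression signature. Plasma level is not on the list, and the link is not a section 2.2 objective. The main exposure question, plasma level against response, is handled with concentration continuous and has stated power of 85%. Conclusions about exposure would not rest on this analysis alone.

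Finally, SNP or mutation status is categorical. Comparing concentration between genotype groups needs no cut, so that part of the extension is not at fault. Nor is using repeated measures with two time points an error; it is merely equivalent to analysing the change.

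**Conclusion.** The concern holds as a mismatch between method and variable. The stated ANOVA suits response but has no place for a continuous, once-measured concentration, and the plan supplies no grouping. If the level were split at the median, the cost would be 0 to about 20 points of power, peaking near a true correlation of 0.27. This assumes 100 evaluable patients, two-sided alpha 0.05, normal levels and a linear relation; the correlation is an assumption throughout. The consequence is limited to one secondary link, and the analyses modelled on it, outside the listed objectives. It is still worth correcting, because the remedy is concrete and removes a choice that could otherwise be made after seeing the data.

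**What to change.** In section 14.2.3, for the drug-level link only, replace the two-way repeated-measures ANOVA with a linear regression.

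- Outcome: the Day 10 change in methylcytosine, or the Day 10 value adjusted for baseline.
- Predictor: continuous plasma concentration, on the log scale if skewed. Leave response out of the main model.
- Report the slope with its 95% CI, and Spearman's correlation as a robustness check.
- Expression profiles against pharmacokinetic data: use concentration as a continuous variable in the same way.
- Categorical SNP or mutation status: compare continuous concentration between the groups.
- Responders against non-responders: keep the ANOVA or t-test.
- If concentration groups are wanted, state the cut-point and the reason for it in advance.

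The cost is SAP wording; samples, patients and software are unchanged. The small downside is the assumption of a linear or log-linear relation, which the rank correlation checks.
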